Data Analytic Plan. Each aim is stated below along with the corresponding data analytic plan. Preliminary analyses and plans for handling missing data are described first.

Preliminary analyses will include: 1) evaluating the psychometric properties of measures, 2) verifying assumptions in analysis of covariance (ANCOVA), general linear model (GLM) and generalized linear mixed model (GLMM), and 3) examining the nature of missing data (e.g., missing at random, MAR). Specifically, we will run descriptive analyses to check for outliers to ensure that distributional assumptions of the planned analyses are appropriate. If not, analogous non-parametric methods will be used. Although all of our primary measures have a favorable psychometric history, we will ensure a satisfactory level of internal consistency for each measure through calculation of Cronbach's alpha.

Missing Data: With respect to missing data, we will follow Bell et al. (2014)'s recommendations which include: 1) make every possible effort to prevent missing data, 2) use the intention-to-treat (ITT) principle and all available data in analyses, and 3) conduct sensitivity analyses that assess the robustness of the results. Thus, our IEs and RAs will review all assessment materials in the presence of teachers, children, and parents to limit the amount of missing data and to help verify the correctness of the data. Because missing data may lead to biased estimation and loss of statistical power if handled inappropriately we will draw upon several approaches if missing data is present (Diggle, Liang, & Zeger, 1994). We will conduct a partial check to determine if the data are missing at random (MAR) by evaluating whether 'missingness' can be explained on the basis of measured variables. Multiple imputation (MI) has been shown to improve upon traditional simple methods for handling missing data (e.g., list-wise deletion, mean substitution; Schafer, 1997). Thus MI ITT results will be compared with other methods such as complete case or maximum likelihood methods in a sensitivity analysis (Soley-Bori, 2013).

Aim #1: To develop and assess the usability, acceptability and feasibility of TAPES, a teacher training to reduce student anxiety. To address this aim, quantitative and qualitative data collected from the DT's initial review of materials and participants' (teachers, children and parents) data in the open trials will be recorded and synthesized in a descriptive manner. The PIs and DT will use this information to refine TAPES' training materials. Additional information regarding feasibility and acceptability will be collected throughout the study (e.g., obtaining reasons for declining initial participation and reasons for drop outs, and evaluating satisfaction). We will review mean scores on measures of satisfaction (e.g., Training Satisfaction and Feedback Questionnaire, TAPES Satisfaction and Feedback Questionnaire) as well as participants' responses to open ended questions on these measures. Moreover comments from the teacher Exit Interviews will enable us to modify individual components in TAPES to enhance its usability, acceptability and feasibility for Stage three. During the pilot RCT in Stage three, ANCOVA will be used to compare TAPES with TAT in terms of usability, acceptability, and feasibility based on the same satisfaction measures. If needed, we will use teacher-specific (e.g., years of teaching experience, teaching efficacy) and child-specific (e.g., age, baseline anxiety severity) as covariates. For example teachers' rating on intervention acceptability will be modeled as y_{ij} = $\mu + \tau_i + B(x_{ij} - \bar{x}_i) + \varepsilon_{ij}$ where *i* indicates teacher-level randomized intervention-training group assignment, say 1 for TAPES, and 0 for TAT, y_{ij} denotes the rating from the jth teacher in group *i* at post training, x_{ij} denotes teacher-specific covariates, and ε_{ij} denotes the unobserved error term. If the null hypothesis $\tau_0 = \tau_1$ is rejected, it implies that teacher's view on

acceptability depends on their assigned group. In addition, weekly data from *Teacher and Child Recruitment Tracker*, *Teacher Time Log*, and *Teacher and Child Retention Tracker* will be used to assess feasibility.

Aim #2: To determine whether teachers can implement the TAPES skills with fidelity/quality. Descriptive statistics will be used to test this aim. We will examine mean scores over time on our fidelity measures (e.g., *S-H Meeting Fidelity and Quality Measure*) to determine the ability of teachers to implement TAPES skills accurately and with high quality. We will also examine which teacher-specific and child-specific variables affect fidelity ratings.

Aim #3 (Primary Outcome): To assess the impact of TAPES, compared to TAT, on teachers' a) *knowledge* regarding student anxiety symptoms and anxiety reduction strategies and b) use of anxiety reduction skills in classroom. To achieve this aim, we will first assess the equivalence of teachers randomized into either TAPES or TAT on baseline teacher (years of experience,

burnout, teacher efficacy; teacher behavior) and child characteristics (e.g., gender, age, baseline anxiety symptoms, classroom functioning). To test the main hypothesis, that teachers in TAPES, compared to TAT, will have higher knowledge about anxiety reduction, we will examine scores on the *Teacher Knowledge Assessment* at post-training, and at the end of school year as outcomes in GLM controlling for teacher pre-training score. Let y_i denote the post-training or end of school year test score of teacher i, x_{i1} and x_{i2} denote teacher i's group assignment and pre-training test score, respectively, and ε_i denote resident term. Rejecting $\beta_1 \leq 0$ and $\beta_3 \leq 0$ in the model: $y_i = \beta_0 + \beta_1 \times x_{i1} + \beta_2 \times x_{i2} + \beta_3 \times x_{i1} \times x_{i2} + \varepsilon_i$ suggests that TAPES teachers' post-training test scores are higher and they have a greater gain in knowledge than TAT teachers. Teacher-specific covariates can be added to the above model as needed. To test the hypothesis that TAPES, compared to TAT, will result in greater use of anxiety reduction skills in the classroom, IE's Classroom Observation of Teachers Skills rating for each pair of teacher and anxious student at baseline, post-intervention, and 3-month follow-up will be modeled in GLMM. Now rating, y_{ijk} are nested within teacher k and student j, who is nested within teacher k, in the multilevel equations: Level 1: $y_{ijk} = \pi_{0jk} + \pi_{1jk} \times \text{timepoint}_{ijk} + e_{ijk}$; Level 2: $\pi_{0jk} = \beta_{00k} + r_{0jk}$ and $\pi_{1jk} = \beta_{10k} + r_{1jk}$; Level 3: $\beta_{00k} = \gamma_{000} + \gamma_{001} \times w_k + u_{00k}$ and $\beta_{10k} = \gamma_{100} + \gamma_{101} \times w_k + u_{10k}$; where w_k denotes teacher k's intervention-training group assignment with e, r, and u representing error terms in the respective levels. Teacher-specific (e.g., years of teaching experience, teaching efficacy) and child-specific (e.g., age, baseline anxiety severity) covariates can be added to Levels 2 and 3 equations as needed. Aim #4 (Secondary Outcomes): To examine the impact of TAPES relative to TAT on student outcomes. Change scores on student mental health (e.g., Spence Children's Anxiety Scale, SCAS) and academic achievement (e.g., Woodcock-Johnson Tests of Achievement) from pre-to postintervention and 3-month follow-up will be modeled as GLMM similar to above in Aim 3. **Exploratory aims**: To examine mediators (proposed in the theory of change, see Figure 1 in Appendix) and predictors and moderators (e.g. Teacher Background Form, MBI-Educators Scale) of TAPES impact on teacher knowledge and behavior. Structural equation modeling (SEM) will be used to explore potential predictors (e.g., baseline teacher burnout as measured by MBI-ES), mediators (e.g., subscale scores from the OSTES) and moderators (e.g., years of teacher experience) on teacher behavior change (e.g., change score on the Classroom Observation of Teachers Skills at pre-, post-intervention and 3-month follow-up). Sub study: Aim #1: Assess the direct and indirect cost of pediatric anxiety among youth enrolled in the TAPES intervention. This aim involves the modification of existing measures of direct and indirect cost. These measures will be administered to parents and teachers at existing TAPES assessment time points (i.e. baseline, post intervention and three-month follow up). Aim #1a: Estimating the cost of pediatric anxiety through direct and indirect costs. Aim #2: To examine the child and parent benefit of TAPES compared to UC. This aim involves estimating the cost of TAPES relative to the UC condition in relation to direct and indirect costs. Exploratory Aim: To examine family demographic factors as moderators of pediatric anxiety cost. **Power Analysis.** Although this is a development study proposing a small pilot RCT, attempts were made to estimate statistical power for the key outcomes based on existing literatures on similar measures (see White et al., 2011 for Teacher Knowledge Assessment and Barrett et al., 2005 for child anxiety using the SCAS). Using Optimal Design version 3.0 calculations for both variables were based on an anticipated enrollment of 20 teachers in each group (and 1-2 students per teacher). We assumed a conservative within-teacher ICC of 0.10 (Eldridge et al., 2004) and

an alpha level was set at .05. Below is a list of minimum effect sizes (calculated as within-group difference in change score, divided by the pooled standard deviation) needed to be detectable with 80% power. With 20 teachers in each group, we will have 80% power to detect the effect size found by White et al. (2011) of d = 1.19 on teacher knowledge. With 30 students in each group, we will have 80% power to detect the effect size found by Barret et al. (2005) of d = .92on child anxiety (effect sizes based on moderately anxious students at pre-post timepoints). Time Table : We are requesting funds for three years. The first six months will be for administrative study start-up tasks (hiring, IRB approval), IE training, and TAPES refinement and review of materials with DT (Stage 1). Months 7 - 20 (Stage 2) will be devoted to recruitment of teachers and students for open trials and further adaptation and refinement of TAPES. Months 21 to 34 will be devoted to implementing the RCT. The final two months (35-36) will be devoted to completing data analyses and manuscript preparation. Personnel: Relevant Expertise of Research Team. The core UCHC research team (Drs. [name] & [name]) along with our consultants have over 20 years of experience in conducting research on the development, evaluation, and dissemination of school-based programs for teachers and school personnel. In addition, the team has extensive experience providing education and training in anxiety reduction skills to school-based and community personnel. Both [name] & [name] moved to UCHC in 2014. In that time they have successfully partnered with 7 CT school districts which now serve as authentic environments for their funded research. They have trained over 40 school clinicians and 17 school nurses as part of their research-exceeding initial recruitment goals. Together they also established the Child/Adolescent Anxiety and Mood Program (CAMP). CAMP conducts community-based research focusing on child and adolescent anxiety and mood disorders, with an emphasis on intervention and dissemination. CAMP now has research coordinators, postdoctoral fellows, and research assistants who work together to recruit research participants and implement studies funded by NIMH and IES. CAMP holds weekly and monthly research meetings that are attended by residents, fellows, and faculty. Currently, CAMP members include 2 faculty, 3 postdocs, 2 Masters level staff, and 8 student research assistants. Finally, Drs. [name] and [name] share responsibility for teaching seminars on child anxiety for psychiatry residents at UCHC. Together, they have given numerous seminars and presentations on childhood anxiety and CBT to a variety of audiences (e.g., parents, teachers, counselors, physicians, and psychiatrists) and have trained school-based clinicians and nurses in the principles and strategies of delivering CBT to anxious youth within schools. These prior experiences have prepared the investigative team to successfully conduct this proposed study. This project reflects a significant and logical next step in this program of research by training teachers in the identification and support of anxious youth. Below is a list of key personnel that will also support this grant, their qualifications, roles, responsibilities, and percent of time and calendar months per year to be devoted to the project are listed below. Evidence of publishing in peer-reviewed scientific journals is documented in the biosketches. Each team member has experience that will ensure the successful implementation of this study.

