studies by the developers, relevant findings revealed that after the teacher-led intervention children had fewer symptoms of anxiety compared to those who received no intervention. In contrast, large RCTs by Miller et al., (2011a; b) and Stallard et al., (2014) found that FRIENDS was not superior to either an attention control condition (story telling such as reading Harry Potter) or to wait-list control groups. A recent qualitative study (Skryabina et al., 2016) reported that teachers were concerned about the feasibility and sustained use of FRIENDS given its high dosage and burden. Reasons for the variations in student outcomes among these studies are unclear but may include the dose and quality of teacher training and fidelity, the complexity of the intervention, and the absence of generalizing skills across home and school settings. In addition, universal interventions for anxiety may not be an efficient use of classroom or teachers' time, as not all youth need these types of interventions. Additional study limitations include the absence of independent (blind) evaluators to assess outcomes, an absence of examining educational outcomes, lack of measurement of changes in teacher behavior, and limited teacher performance feedback and coaching to increase fidelity and quality of implementation. In sum, teacher training in anxiety management is rare. Although data indicate that teachers are capable of implementing classroom-based interventions with fidelity (Durlak et al., 2011), studies on universal models for anxiety are flawed and indicate that a novel teacher training is needed for students with elevated anxiety. The current proposal addresses these shortcomings (see Logic Model Figure 2 in Appendix).

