Overview: Design and Methods. This three-year development project consists of 3 stages. **Stage one** (months 1-6) involves establishing a Development Team (DT) that will review the initial draft of TAPES and provide feedback to ensure that TAPES is acceptable to teachers and feasible for the school setting. **Stage two** (months 7-20) involves two successive open trials of the TAPES protocol with 15 teachers and 20 children. This stage will allow for "trial runs" of the training to assess feasibility, acceptability and utility of the training. Data and qualitative feedback gleaned during the first open trial will inform modifications for the second open trial. We will present and discuss data with the DT after each open trial. We will also ask 5 teachers from open trial 1 to test out the revisions for open trial 2. Based on knowledge gained in this stage, appropriate modifications will be made for stage three. **Stage three** (months 21-34) involves a pilot RCT using a randomized controlled design comparing TAPES to the Teacher Anxiety Training (TAT). TAT (developed by the PIs for use in other studies and described below) will be used to represent "typical" teacher professional development training. The RCT will be conducted in three phases. Phase 1 consists of recruiting, randomizing, and training

teachers in either TAPES or TAT. Also during this phase (but after the training), teachers will recruit anxious children and study staff will screen and evaluate them to determine eligibility. In Phase 2 teachers will implement TAPES or TAT. Phase 3 involves a post-intervention (after 8 weeks) and a three-month follow-up assessment of the primary (teacher behavior) and secondary (child) outcomes. Trained independent evaluators (IEs) will assess primary outcomes (teacher behavior). The culmination of these iterative stages will be a final version of the training that will be ready for evaluation in a larger efficacy trial.

DETAILED DESCRIPTION OF EACH STAGE

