-Teacher Knowledge Assessment is a 26-item short answer and multiple choice test of anxiety reduction strategies to gauge teachers' prior knowledge and the effectiveness of training. This measure was adapted from an existing knowledge assessment test for school clinicians, which showed an increase in knowledge pre to post-training ([name] et al., 2008).

-*Classroom Observation of Teachers Skills* is a form completed during direct observations of the teacher during normal class activities (e.g., math or reading). The observations are coded by tallying the frequency of specific behaviors that have a positive or negative impact on student anxiety. Using a 5 point Likert scale, observers provide an overall rating of teacher's behavior in both domains.

Usability Measures- The following measures assess whether teachers can understand and learn how to use the skills and whether they can implement the skills effectively and efficiently.

- Teacher Knowledge Assessment (above) will assess ability to learn skills.

- *Classroom Observation of Teachers Skills* (above) will assess use of skills in the classroom. -*Teacher and Child Recruitment Tracker* will be used to record recruitment of teachers/children as well as obstacles to recruitment. Obstacles will be addressed in team meetings and with DT. -*Teacher Time Log* is a form completed by teachers to log the amount of time spent using TAPES/TAT skills with each study student.

Feasibility Measures – The following measures assess whether the training skills can be implemented within an authentic school setting.

-Training Satisfaction and Feedback Questionnaire ([name] et al., 2008, 2011) is a 16-item measure completed anonymously by teachers who rate the helpfulness of training content and format (e.g., role play, videos), overall satisfaction and perceived helpfulness of TAPES/TAT skills for students with anxiety, and their preparedness to conduct conjoint meetings using a 4-point Likert-type scale (1 = not at all helpful to 4 = very helpful). Open-ended questions ask about the most/least helpful aspects of training and suggestions for improvement.

- *TAPES & TAT Satisfaction and Feedback Questionnaires* ([name] et al., 2012) will be adapted for this study from an existing questionnaire and will assess satisfaction and helpfulness of skills used with anxious and in the classroom.

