-Exit Interviews will be conducted with teachers after completing the TAPES program with a student. The PIs will arrange a time to talk with teachers (20 minutes) to obtain qualitative information about perceived barriers to using TAPES, experience implementing TAPES, perceived impact on students, etc. and or suggestions for future implementation. These interviews will take place during the open trials and inform revisions for the RCT.

- *Teacher and Child Retention Tracker* will be used to record the rates/reasons for attrition for both teachers and students and will be discussed weekly in team meetings and with the DT. -*Satisfaction Forms, Meetings 1-5* will be administered to teachers, parents, and students to assess satisfaction with each school-home meeting.

Fidelity of Implementation Measures – The following measures, described above, will assess adherence and quality of implementation of TAPES:

- S-H Fidelity and Quality Measure (Meetings 1-5) is a form assessing the fidelity and quality of TAPES skills based on audio-recorded school-home meetings. The goals of each meeting are

rated for adherence (Was goal accomplished? Yes/No) as well as quality of implementation (1 = Poor to 4 = Very Good), which reflects the accuracy of the presentation, use of elaboration and student-specific examples, and assessment of parent/student understanding.

- *Teacher S-H Meeting Summary Form* is a 16-item measure completed following conjoint meetings. This checklist contains items that measures parent and student involvement, assesses barriers to use, and whether goals were accomplished.

- *Classroom Observations of Teachers Skills* (see above) will be used to assess fidelity. Teacher and Child Measures Linked with TAPES Theory of Change. Several measures will be collected to assess factors that may influence fidelity of TAPES skills and/or are directly linked to the proposed theory of change:

- *Student-Teacher Relationship Scale* (STRS; Pianta, 1992) is a 15-item scale with good psychometric properties that will assess the quality of the teacher-child relationship.

- *Parent-Teacher Relationship Scale* (Vickers & Minke, 1995) is a 24-item measure of teacherparent relationship quality. The measure has good psychometric properties (Dawson & Wymbs, 2016).

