- School Attendance, Discipline, and Parent's Missed Work – This questionnaire will obtain information from parents about their children's school attendance, disciplinary actions taken against their child and the amount of work that they have missed due to anxiety related reasons. This will be completed at baseline and all follow up assessments.

- *Child Health Utility Index (CHUD)* – This 9-item questionnaires assess the student's overall health and functioning in various domains. It is commonly used in the context of intervention cost-effectiveness research and demonstrates adequate psychometric properties (Furber & Segal, 2015).

Instrument	Purpose	Rater	Time	Completion
			Point	time
Primary Outcomes: Teacher Knowledge and Skills				
Teacher	Assess teacher knowledge of anxiety	Teacher	BL, PO	10 min
Knowledge	reduction strategies			
Assessment				

Table 1 Assessment of Study Measures

Classroom	Assess accurate use of skills by	IE,	BL, PO,	30 min
Observations of	teacher in classroom	Teacher	FU	
Teachers Skills				
Usability Measu	res			
Teacher	Assess teacher ability to learn new	Teacher	BL, PO	10 min
Knowledge	information			
Assessment				
Classroom	Assess whether teachers can use	IE	Pre-	30 min
Observation of	skills		Training	
Teachers Skills			, BL,	
			PO, FU	
Teacher and	Assess teacher ability to identity	IE	WKLY	5 min
Child	anxious youth			
Recruitment				
Iracker		TT 1		- ·
Teacher Time	Assess number and length of school-	Teacher	WKLY	5 min
Log	nome meetings and other			
	interactions with the study child			
Eassibility Maas				
Training Meas	Assass togeher training satisfaction	Tanahar	Doct	5 min
Satisfaction and	as marker of willingness to use the	reacher	r USI training	5 11111
Feedback	TAPES or TAT intervention or		uannig	
nuestionnaires	skills			
TAPES	Assess perceptions of feasibility	Teacher/	PO	5 min
Satisfaction and	satisfaction and helpfulness of	Parent/	10	5 11111
Feedback	intervention	Child		
Ouestionnaires				
Satisfaction	Assess parent and teacher	Teacher/	WKLY	5 min
Forms, Meeting	satisfaction and perceptions of	Parent		
1-5	helpfulness of each meeting			
 		 	*****	- ·
Satisfaction	Assess child satisfaction and	Child	WKLY	5 min
Forms, Meeting	perceptions of helpfulness of each			
2-5	meeting			
Exit Interview	Document teachers experience in	Ы	РО	20 min
	program: perceived barriers, etc.		10	
Teacher and	Assess interest and ability to	IE	WKLY	5 min
Child Retention	implement intervention within			

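### No stated rule masks the evaluators who rate the primary classroom-observation outcome, and some of their assigned duties can reveal the teacher's arm

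*Combined protocol and SAP*

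**What the plan says.** The Overview: Design and Methods section states: "Trained independent evaluators (IEs) will assess primary outcomes (teacher behavior"). In the Data Analytic Plan, Aim 3, the variable modelled for use of skills is the "IE's Classroom Observation of Teachers Skills rating for each pair of teacher and anxious student", taken at baseline, post-intervention and 3-month follow-up. The measure combines a tally of specific behaviours with a global judgement: "Using a 5 point Likert scale, observers provide an overall rating of teacher's behavior in both domains".

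Table 1 gives the IE other work as well. The IE is the weekly rater of two forms:

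- **Teacher and Child Recruitment Tracker.** Its purpose entry begins "Assess teacher ability to identity" and concerns anxious youth. The Usability Measures text says it also records obstacles to recruitment, which go to team meetings and the Development Team.
- **Teacher and Child Retention Tracker.** Its purpose entry begins "Assess interest and ability to" and goes on to implementing the intervention within the school's constraints. The Feasibility Measures text says it "will be used to record the rates/reasons for attrition for both teachers and students and will be discussed weekly in team meetings".

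The Missing Data paragraph adds that IEs and RAs will go through all assessment materials with teachers, children and parents present.

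The only mention of blinding in the available text is in the Significance section, which lists among the limits of earlier studies the "absence of independent (blind) evaluators to assess outcomes". The same paragraph closes by saying that the proposal addresses these shortcomings.

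**The concern.** Independence and masking are different things. An evaluator can be independent of delivery and still know which training a teacher received. The protocol treats masking as important when it judges other trials, but in the available text it sets no procedure to secure it here.

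This goes beyond a missing sentence, because the plan gives the outcome rater duties that work against masking. An IE who records each week why a teacher has trouble recruiting, implementing or staying in the study is well placed to learn which programme that teacher is in. If the same IE then gives an overall 5-point rating of the teacher's classroom behaviour, expectation can move the score towards TAPES. A difference produced in that way would be hard to tell from a real training effect, and it would fall on one of the two primary outcomes of a pilot meant to justify a larger efficacy trial.

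**Working it through.** The documents give no figure for this point, so there is none to reproduce. The check is mainly textual.

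**1. Where a masking rule would be expected**

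| Place | What it gives on IE masking |
|---|---|
| Significance | Faults earlier trials; general promise to address shortcomings |
| Overview: Design and Methods | IEs are trained and independent; masking not mentioned |
| Randomization | 1:1 by teacher, 20 per arm; plan generated before teachers are identified; nothing on who knows the result |
| Independent Evaluator (IE) Training | Didactic training, interview review, rater reliability; no masking element |
| Measures and Table 1 | Raters and time points only |
| Data Analytic Plan | No masking and no check on it |

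**2. How the arms differ.** TAPES has a full training day, about five conjoint meetings over 8 weeks, weekly consultation and in-class coaching. TAT is a 3-hour didactic session. Information about what a teacher is implementing, or why implementation is hard, can therefore point to the arm.

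**3. Which IE duties could carry that information**

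- *Both trackers.* IE, weekly. The measures are for Stages 2 and 3, so the RCT is included.
- *Review of all assessment materials.* Read literally, this covers the satisfaction forms for meetings 1 to 5, the teacher's meeting summary form and the Teacher Time Log, which Table 1 says captures school-home meetings. Teachers or families complete these forms, but an IE who reviews them would see the arm directly.
- *Service Utilization Form.* IE-rated in Table 1, and to be extended for the sub-study to school-based services and teachers' time. It is a possible further route.

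**4. When the IE could learn the arm.** Under Stage 3, Phase 1, teachers are randomized and trained before the IE's baseline evaluation of the child. All three visits in the Aim 3 model can therefore be affected.

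**5. Illustration of size.** The shift *b* (in SD units, towards TAPES) is an assumption. Inputs from the documents are n = 20 teachers per arm and alpha = 0.05, taken as two-sided because the plan does not state sidedness. For a two-sample t test with no true effect:

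- df = 2 × 20 − 2 = 38; critical value 2.024
- noncentrality = b × √(20/2) = b × 3.162
- rejection rate = probability that a noncentral t exceeds 2.024 in absolute value

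| b (SD) | Noncentrality | Rejection rate |
|---|---|---|
| 0 | 0 | 5.0% |
| 0.1 | 0.316 | 6.1% |
| 0.2 | 0.632 | 9.5% |
| 0.3 | 0.949 | 15.2% |
| 0.5 | 1.581 | 33.8% |

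**6. Link to the planned model.** In the Aim 3 equations, group acts on the intercept (γ001) and on the slope over time (γ101). A rater shift that is equal at every visit enters γ001 and cancels from γ101. A shift that appears or grows after baseline, as it might if the arm became known through weekly records, enters γ101. The plan does not name the coefficient to be tested, so the table above cannot be carried over to it.

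**The case against.** The strongest reply has five parts.

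- **Masking may be intended, or written elsewhere.** The Significance section uses independent and blind almost as synonyms and says the shortcomings are addressed. The personnel section introduces a list of roles and responsibilities, and part of that section was not available for this review. This stands as a limit: a reader might infer that masking is specified nowhere, but only the available text can be vouched for. An intention in the background section is still not an operating rule.
- **The trackers may not show the arm.** A reader might infer that, followed as written, the plan makes the rater learn the allocation. The documents do not support that. They do not say that the trackers show the arm, that IEs attend the team meetings, or that the IE who tracks a teacher also observes that teacher. What stands is that nothing prevents any of these, and that the listed content can point to the arm.
- **Meeting activity is recorded by others.** The time log and meeting summary are completed by teachers, and meeting fidelity is rated by a principal investigator. This is correct, but the duty to review all assessment materials brings the teacher and family forms back within the IE's sight.
- **The outcome is not purely subjective.** Behaviour tallies leave less room for expectation than the overall rating. This stands, and it is why the concern lies mainly with the 5-point judgement.
- **The figures do not describe the planned analysis.** This also stands. The shift is assumed, and the planned model has three levels and three visits. A reader might infer that no analysis could remove the bias, but a shift constant across visits would cancel from the slope term.

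**Conclusion.** The point holds as a risk that the plan leaves open and partly creates through its assignment of duties. It is not a demonstrated unmasking. In the available text no operating rule masks the IEs who rate the primary classroom observation. The weekly trackers and the review of all materials can reveal the arm, and knowing it can bias the rating towards TAPES. The link from these duties to knowledge of the arm is an inference from the visible difference between the programmes.

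The point is confined to the observation outcome among the primaries, because the Teacher Knowledge Assessment is completed by the teacher. IEs also rate the diagnostic interview and the global severity and functioning scales, so masking would protect those student outcomes too.

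The size cannot be derived from the documents. The rates of 9.5%, 15% and 34% hold only for assumed shifts of 0.2, 0.3 and 0.5 SD in a simple t test, and they are not a property of the planned model. For a pilot, this is a cheap improvement worth making before the RCT stage.

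**What to change.** 1. State in the Randomization and IE Training paragraphs that IEs are masked to teacher allocation, and say who holds the allocation.
2. In Table 1, change the rater of both trackers from IE to RA. RAs already complete the School Records Form and share the review of materials.
3. In the Missing Data paragraph, give the review of arm-revealing forms (meeting satisfaction forms, meeting summary, time log) to RAs only. Do the same for any items on the Service Utilization Form that would show the programme.
4. Keep IEs out of meetings, or parts of meetings, where tracker content is discussed.
5. Record any unmasking, with its date and source. Asking each IE to guess the arm at the post visit is an optional addition.
6. In the same edit, reconcile the rater of the classroom observation: the primary-outcome row of Table 1 lists both IE and teacher, while the usability and fidelity rows list the IE alone.

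The cost is two 5-minute weekly forms moved to existing staff, a few sentences of text and some separation of staff schedules. Masking may still be imperfect, since teachers or families may mention the meetings and observed classroom behaviour may itself suggest the arm. That is why unmasking should be recorded.
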